## 2.2. **Rationale for Study Design**

There is a clinical need to develop a non-invasive fetal monitor that has greater reliability than both the Toco/Doppler monitor and first-generation EMG/ECG fetal monitors. In response, PreTel has created the regional contraction uEMG/ECG fetal monitor. PreTel's fetal monitor is based on new understanding of uterine physiology, which confers the following advantages: 1) 5X larger EMG signals; 2) ability to localize uterine activity to specific regions of the uterus; 3) an analysis that is based on function of the whole organ. Together, we hypothesize that PreTel's fetal monitor will provide more accurate reporting of contractions, and the ability to non-invasively separate contractions of true labor from false labor.

### 3. CHARACTERISTICS OF THE RESEARCH POPULATION

#### 3.1. Subject Characteristics

##### a) Number of Subjects:

We plan to recruit up to 50 study subjects to complete the entire 60 minutes of testing and consent to have their chart reviewed after delivery to collect all objective outcome data as outlined in our study plan. Data from those who start the uEMG recordings but are unable to complete the full duration will still be analyzed so long as the reason for their withdrawal is not secondary to their withdrawal of consent. Those who withdraw consent will be excluded for data collection and analysis.

##### b) Gender and Age of Subjects:

Pregnant females over 24 weeks gestation age, and age 18 or older (to avoid consenting minors - we do not wish to study pregnant women under the age of 18).

##### c) Racial and Ethnic Origin:

Women will not be excluded on the basis of racial or ethnic origin. The patients enrolled in the study should represent the distribution of racial and ethnic origins encountered at URMC.

##### d) Vulnerable Subjects:

The study will include pregnant women. There is no way to perform this study in a non-pregnant population. Since the “intervention” is observational only, there is minimal risk and no need for additional safeguards.

#### 3.2. Inclusion and Exclusion Criteria

##### a) Inclusion Criteria:

- Age 18 or greater
- At least 30 weeks gestation
- English reading and speaking
- Female gender
- Singleton fetus
- Experiencing contractions and <3cm dilated
- Patients’ primary complaint or primary reason for seeking evaluation is uterine contractions and/or suspected labor.
- May be undergoing induction or augmentation of labor (Induction or augmentation refers to any mechanical or medical technique except artificial rupture of membranes (AROM). Subjects undergoing AROM alone, without other induction or augmentation techniques being used concurrently, will be included as a special category within spontaneous labor)
- May have clinical indications for internal monitoring (IUPC and/or FSE)
- Subjects may have intermittent fetal and uterine monitoring as a part of their overall birth plan; however for the 60 minutes of monitoring with EMG required for participation in the study, the subject must be willing to utilize continuous uterine and fetal monitoring.
- Subjects may be scheduled for induction of labor or Cesarean section delivery
- Patients must be able to review and sign informed consent to participate in the study.
- Trial of labor after cesarean section are eligible for participation
- Subjects with premature rupture of membranes in whom labor is augmented are eligible for inclusion in the study

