### 5. METHODS AND STUDY PROCEDURES

#### Monitoring before and during scheduled induction or Cesarean Section.

In many cases, patients present to labor and delivery for a clinically-indicated induction of labor or Cesarean Section. Following consent, study monitoring will be performed prior to initiation of labor induction or Cesarean Section. If the subject and the research personnel agree, study monitoring may be periodically discontinued, and restarted at a later time without requiring subject withdrawal.

For a scheduled induction, monitoring will occur when the patient is contracting and <3cm dilated. Recordings may be stopped and restarted multiple times for a single subject if needed.

For cesarean sections, the subject can undergo 60 minutes of EMG monitoring just prior to her planned cesarean delivery, if this would not otherwise delay delivery.

Triage patients:

Some patients (not scheduled for delivery), present to labor and delivery for evaluation of labor. They may perceive contractions, but may or may not be in active labor as defined by cervical change, or may or may not have experienced rupture of membranes.

Some patients present with rupture of membranes or a small abruption, in the preterm setting, and for these cases, the decision is usually made to not augment or induce labor. Alternatively, in the term setting, the decision to proceed with delivery via augmentation or induction for those noted conditions, is often made. For cases where the decision to not induce or augment labor is made, study monitoring can initially be performed for 60 minutes. In cases where the decision to deliver via induction, augmentation or expectant management is made, the protocol will be the same as in the sections describing monitoring before and during scheduled induction of labor.

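### Section 3.2 requires contractions or suspected labor as the reason for coming, yet sections 4.1 and 5 enrol women who come for a scheduled induction or cesarean, and their labor label can then be set by the schedule

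*Combined protocol and SAP*

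**What the plan says.** Three items in the inclusion list of section 3.2 a) bear on this point. The woman must be "Experiencing contractions and <3cm dilated". Her "primary complaint or primary reason for seeking evaluation is uterine contractions and/or suspected labor". A third item is permissive: "Subjects may be scheduled for induction of labor or Cesarean section delivery". Neither of the first two carries an exception for scheduled cases.

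Section 5 opens with women for whom the visit is the procedure itself: "patients present to labor and delivery for a clinically-indicated induction of labor or Cesarean Section". For them, "study monitoring will be performed prior to initiation of labor induction or Cesarean Section". The conditions then differ by procedure:

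- Induction: "For a scheduled induction, monitoring will occur when the patient is contracting and <3cm dilated".
- Cesarean: "the subject can undergo 60 minutes of EMG monitoring just prior to her planned cesarean delivery". The only proviso is that delivery is not delayed.

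Section 5 describes women who come for a labor evaluation as a separate triage group who are not booked for delivery. Section 4.1 likewise lists arrival for induction or cesarean as an alternative to arrival with suspected labor. Section 2.1 mentions only women approached when they present for labor evaluation.

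Two parts of section 14 depend on who is enrolled. Section 14.1 arrives at 23 women with 10 contractions each and recruits up to 50. Section 14.2 labels a woman in labor if she delivers within 24 hours, not in labor if she delivers at 72 hours or later, and transitioning in between.

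**The concern.** The text gives opposite answers about the same woman. If she comes for a booked cesarean, the primary-reason criterion excludes her, while sections 4.1 and 5 recruit and record her. Two staff members screening from this protocol could decide differently, and the mix of women enrolled would depend on which section they followed.

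The mix matters for the labor result. Section 14.2 starts from women whose labor status is unclear at testing and uses time to delivery to settle it. For a woman recorded shortly before a planned delivery, time to delivery is largely decided by the booking. The outcome label then says little about whether her uterus was in labor during the recording. Pooling her with the triage women makes the synchronization factor (SF) look better or worse for reasons unrelated to the device.

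A smaller matter is the contraction count. A recording in a woman who is not contracting supplies no reference contractions for sensitivity or timing, yet nothing in section 14.1 stops it counting toward the 23.

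**Working it through.** The check is mainly a comparison of texts. The only arithmetic is the reserve in section 14.1.

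**Step 1. Eligibility by entry route.**

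| Route | Primary-reason criterion (3.2) | Contracting and under 3 cm (3.2) | Enrolled by 4.1 and 5 |
|---|---|---|---|
| Labor evaluation | Met | Required; no conflict | Yes |
| Scheduled induction | Not met as written | Required, and repeated in section 5 | Yes |
| Planned cesarean | Not met as written | Required, but not repeated in section 5 | Yes |

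The conflict over the reason for coming covers both scheduled routes. The gap over contractions and dilation concerns planned cesarean only.

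**Step 2. Can the permissive item remove the conflict?** Taken alone, it could mean a woman with a booked delivery who first comes in contracting. Section 5 does not allow that as the only meaning, because it describes women who arrive for the procedure and sets the labor-evaluation group apart as not booked for delivery.

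**Step 3. Effect on the labor label.** The SF values below are the illustrative ones under Endpoint 1.4.

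- A woman is recorded just before a planned cesarean and her SF stays below 0.25. The prediction is not in labor. She delivers within 24 hours, so her label is in labor and the prediction is scored as wrong, although it may describe her uterus correctly.
- A woman is contracting when recorded before induction and her SF stays above 0.75. The prediction is in labor. If she delivers within 24 hours, it is scored as right, although the induction may have produced the timing.

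The two cases push in opposite directions, so the documents fix neither the sign nor the size of the net effect.

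**Step 4. Does the CRF already separate these women?** Only in part. Section 2.1 collects whether labor was spontaneous or induced/augmented, the mode of delivery, and its date and time. It does not collect the reason for coming. A woman who arrived contracting and was later augmented or delivered by unplanned cesarean can look the same on those items as a scheduled case.

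**Step 5. Which endpoints need reference contractions?**

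- Needed: sensitivity (1.3 and 2.4a), timing (2.4b), and SF against IUPC peak strength (1.4).
- Not needed: specificity (1.3), where contraction-free time is where false positives appear; 10-second epoch interpretability (2.3), which needs a valid IUPC signal; and the heart-rate endpoints.

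**Step 6. The reserve.** The plan's figure reproduces: 23 × 10 = 230 contractions. With 50 women recruited, 50 − 23 = 27 sessions (27/50 = 54%) could lack reference contractions before fewer than 23 women remained. That is the whole reserve, and section 14.1 assigns it to incomplete sessions, so the true margin is smaller by however many of those occur.

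**The case against.** The strongest reply is that section 5 is procedural and does not waive section 3.2. Section 4.2 limits consent to women who fit the inclusion criteria, so the contraction and dilation requirement still governs planned cesareans even though section 5 does not repeat it. That is a fair reading, and for contractions it reduces the problem to an omission. It does not help with the primary-reason criterion: section 5's first group is defined by coming for the procedure, and strict application of 3.2 would exclude the very women that subsection describes.

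A second reply is that section 1.1 covers non-laboring as well as laboring patients, so scheduled women may be wanted. That is also fair, and it argues for saying so explicitly.

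A reader might also infer several stronger points that the documents do not support:

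- *That inductions are recorded without contractions.* Section 5 keeps the condition for them. Its two induction sentences are compatible if the woman is already contracting before induction starts.
- *That contraction-free recordings are worthless for the contraction endpoints.* They inform specificity in 1.3 and, where an IUPC is in place, interpretability in 2.3. Section 1.2 itself names false-positive contractions as a weakness of EMG.
- *That the study will fall short of 23 informative women.* No document gives the share of scheduled cases or the share of those not contracting, and the reserve is large.

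Finally, reporting by route does not correct the label given to scheduled women. It does let the result in the labor-evaluation group be read without them.

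**Conclusion.** The contradiction stands. As written, a woman who comes for a scheduled induction or cesarean does not meet the primary-reason criterion in section 3.2, yet sections 4.1 and 5 enrol her. For planned cesarean, section 5 also leaves unstated whether she must be contracting and under 3 cm dilated.

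The main statistical consequence is that the 24-hour rule in section 14.2 can label scheduled women in labor because of the booking. This rests on one assumption: that deliveries booked at the time of recording usually take place within 24 hours. That is close to certain for a recording made just before a cesarean and less so for an induction. The size depends on the number of scheduled women, which the documents do not give. Across the possible range, it is nil if none are enrolled and grows with their share of the 50.

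The effect on the contraction count is secondary, and no shortfall is demonstrated. This review does not say which eligibility rule is right, only that the sections must agree.

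**What to change.** 1. Reconcile sections 2.1, 3.2, 4.1 and 5 so that the eligibility of scheduled cases is stated once, including whether the primary-reason criterion and the contraction and dilation criterion apply to them. Narrowing section 5 or writing an explicit route into section 3.2 would each achieve this; the choice is the sponsor's.
2. If scheduled cases are kept, add one CRF field for entry route (labor evaluation or scheduled) and report contraction, SF and labor-prediction results by route.
3. In section 14, base sensitivity, timing and SF-strength analyses, and the count of 23 women and 230 contractions, on sessions with reference contractions. Keep contraction-free sessions for specificity, interpretability and the heart-rate endpoints.

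Cost: protocol wording and one CRF field. Fewer of the 50 may count toward the contraction-sensitivity total. No woman already recorded need be discarded for lack of contractions.

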**b) Exclusion Criteria:**

- Twins, triplets and larger number multifetal gestations
- Age less than 18 years
- Humans without a uterus
- Non-English reading and/or speaking
- Significant uterine anomalies such as didelphys or bicornuate uterus (women with small, clinically insignificant anomalies such as uterine fibroids are not excluded).
- Participants cannot be participating in any other research study or protocol regarding uterine contraction monitoring during the same study period as required for our study.
- Known allergy to ECG pad adhesive
- Non-living fetus
- Major fetal malformation
- Fetal distress, or other indications for emergent delivery

**3.3. Discussion of Subject Population**

This study can only be performed on pregnant subjects. To avoid the need for the consent of subjects under the age of 18 who are pregnant, minors will be excluded from this study.

**4. SUBJECT IDENTIFICATION, RECRUITMENT AND CONSENT**

**4.1. Method Of Subject Identification And Recruitment**

Women who present for routine obstetrical care at URMC affiliated outpatient sites (i.e., Women's Health Practice, University OBGYN, Strong Perinatal Associates, and Special Care Clinic) and those women who present for evaluation of labor at URMC will be screened for participation. Screening will be performed by regular hospital staff (resident physicians, nurses, other obstetricians) or study coordinators screening subjects on L&D. Patients who meet criteria will be offered participation in the study. Not all patients who meet criteria will be offered the study. This will largely depend on the availability of research personnel (availability of a study coordinator to consent the subject) and the acuity on Labor and Delivery at the time of presentation.

BMI stratification will require us to enroll equal numbers of patients in each BMI category.

Subjects approached in the office by a study coordinator prior to their presentation in labor will be eligible to complete the consent prior to being in labor, presenting to URMC with suspected labor, presenting for an induction of labor or cesarean section. A note regarding their consent to participation in the study will be placed in their medical record in the Provider "Sticky Note" to inform hospital staff that the subject is in the study (see risk section). This notification will help to facilitate contacting the study coordinator at the time of the subjects' hospital admission.

All potential subjects will be told that we are investigating new methods to monitor the baby's heart beat and uterine contractions during labor, and that they will simultaneously receive standard-of-care clinical monitoring. Patients who refuse participation will receive the standard-of-care.

The date and time that the subject, or the subject's authorized representative, signs the informed consent form and a narrative of the issues discussed during the informed consent process will be documented in the subject's study case history. The Primary Investigator at URMC ([name]) will retain the original copy of the signed informed consent form and a copy will be provided to the subject or the subject's authorized representative.

Study personnel will also record the participants name and Medical Record Number in an I-Drive password protected database in order to select a unique identifier code, which will be used to label all EMG data and record the study data points as outlined above. Each subject will be coded per the following: mm/dd/yy-xx, where mm/dd/yy is the date of study, and xx refers to subject #01 through 50. All data sets, including the EMG tracings, fetal ECG tracing, and the CRF will be coded by the number.

Recording of the MRN and name is necessary in order to facilitate accessing the subjects' delivery records after completion of the study. Electronic accessibility to this key is necessary so that study investigators can enroll patients in triage, L&D and the birth center as well as at the out-patient URMC-affiliated obstetric offices, which are not in close proximity to the locked office of the PI.

All collected data will be recorded on Case Report Forms (CRF), attached in appendix 2. These will be copied and sent to [name] (recipient of NIH SBIR grant). A copy will be saved at URMC in the locked office of the local PI [name].

At the completion of the study all patient-identifying information will be kept in a secure locked filing cabinet. The time line for destruction will be no less than 10 years following study completion based on institutional protocol.

#### 4.2. **Process of Consent**

Once a potential participant has been identified as fitting the inclusion criteria, without any exclusionary criteria, the study will be verbally described to the potential participant to assess their interest in participation. This will be done by the study PI or a study coordinator, who will then provide the subject with written information regarding the study and complete the consent form with the subject. The individual obtaining consent will be selected based on the time of day and their subsequent availability. The entire consent form will be reviewed with the participant and the participant will be given additional time to re-read the forms and ask any questions. The participant will then sign the consent form if they are still interested in participating. Consent forms will be stored in the locked office of [name].

### 5. METHODS AND STUDY PROCEDURES

#### Monitoring before and during scheduled induction or Cesarean Section.

In many cases, patients present to labor and delivery for a clinically-indicated induction of labor or Cesarean Section. Following consent, study monitoring will be performed prior to initiation of labor induction or Cesarean Section. If the subject and the research personnel agree, study monitoring may be periodically discontinued, and restarted at a later time without requiring subject withdrawal.

For a scheduled induction, monitoring will occur when the patient is contracting and <3cm dilated. Recordings may be stopped and restarted multiple times for a single subject if needed.

For cesarean sections, the subject can undergo 60 minutes of EMG monitoring just prior to her planned cesarean delivery, if this would not otherwise delay delivery.

Triage patients:

Some patients (not scheduled for delivery), present to labor and delivery for evaluation of labor. They may perceive contractions, but may or may not be in active labor as defined by cervical change, or may or may not have experienced rupture of membranes.

Some patients present with rupture of membranes or a small abruption, in the preterm setting, and for these cases, the decision is usually made to not augment or induce labor. Alternatively, in the term setting, the decision to proceed with delivery via augmentation or induction for those noted conditions, is often made. For cases where the decision to not induce or augment labor is made, study monitoring can initially be performed for 60 minutes. In cases where the decision to deliver via induction, augmentation or expectant management is made, the protocol will be the same as in the sections describing monitoring before and during scheduled induction of labor.

For both the preterm or term subjects who present to triage, there is the possibility that they may not ultimately progress in labor. These subjects are also eligible for an EMG study session for 60 minutes while their labor status is being evaluated. If they are deemed to not be in labor (i.e. no cervical change) and are discharged (or admitted for extended monitoring, as may occur in the preterm setting or at term for “therapeutic rest”), they will not be excluded from analysis, and they will be allowed to participate in another session either when they begin laboring (i.e. if admitted) or if they are discharged and then return to Triage for another labor evaluation. Recordings may be stopped and restarted multiple times for a single subject if needed.

During the 60+ minutes of EMG pad placement, subjects must also have standard tocometry monitoring and fetal heart rate monitoring. The standard monitoring can consist of either external tocodynamometry (Toco) or an intra-uterine pressure catheter (IUPC) and either external Doppler monitoring of the fetal heart rate or a fetal scalp electrode (FSE). Which type of monitoring is used will be at the discretion of her regular obstetric care team and will not be altered by participating in the study (i.e., the study will not require the patient to have internal monitoring IUPC/FSE). Participation during the 60 minutes of recording does however require some form of continuous monitoring, and therefore subjects desiring intermittent fetal heart rate auscultation or intermittent palpation for contractions, will not be eligible for participation unless they are willing to have standard monitoring for the duration of the study period. Clinical decisions will only be made based on standard uterine and fetal monitoring and examinations.

Uterine EMG recordings, along with the fetal monitoring paper record, will be sent to PreTel. Assessment of the recordings for uterine contractility and fetal heart rate will then be performed by those investigators trained in the analysis ([name]). The EMG data will be compared to the tocometry data to determine correlation or “R” value.

The Case Report Form (CRF) (Appendix 2) will be completed for each subject enrolled in the clinical study. The local investigator will review, approve and sign/date each completed CRF; the local investigator’s signature serving as attestation of the local investigator’s responsibility for ensuring that all clinical and laboratory data entered on the CRF are complete, accurate and authentic.

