### **First generation EMG/ECG fetal monitors**

Because of these potential benefits, fetal monitors using EMG/ECG technology (including display of maternal heart rate) have been developed. These first-generation devices use traditional, circular ECG pads to record fetal ECG, maternal ECG, and uterine signals. However, ECG pads were specifically designed to record heart signals, and yield only small signals from the uterus. Small signals require a moderate amount of data processing suggesting sub-optimal reliability. Reporting of false positive contractions is a problem with EMG reliability that is not seen with legacy methods, and this creates a problem that clinicians have no experience in accommodating.

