## **2. STUDY DESIGN**

### **2.1. Overview**

This is an NIH SBIR feasibility and efficacy study. This study seeks to validate the reliability of the PreTel Regional Contraction uEMG/ECG Fetal Monitor in accurately determining contraction and the fetal heart rate. The study also seeks to validate the reliability with which the monitor is able to determine true labor contractions from false labor contractions. The study will achieve these goals by utilizing the PreTel Regional Contraction uEMG/ECG Fetal Monitor concurrently with standard fetal and uterine monitoring prior to and during labor.

Patients will be approached as they present for evaluation of labor in Triage and Labor and Delivery. After obtaining consent, we will have the subject sit, slightly reclining. We will place up to 15 EMG electrode pads over her abdomen, spanning most of the surface of the uterus, plus one ground electrode. The arrangement of the electrodes will be documented. If the patient consents to photo-documentation of the arrangement, then a de-identified photo of the sensor arrangement will be taken and stored electronically. The purpose of the image is to assess the

overall abdominal coverage of all EMG/ECG sensors and the placement of the legacy (traditional) monitors. The photograph may be taken before, during or after the completion of testing, so long as it accurately represents the locations of the area and pad sensors of the study device, and the Toco and Doppler of the legacy devices. Should significant adjustments of the study or legacy recording devices occur, such that the locations change, additional photographs may be taken to provide additional information of sensor locations at different times during testing. If the subject requests that a photograph not be taken, or if there is a technical reason that a photograph cannot be obtained, no photograph will be taken, and the subject will continue as a research subject (i.e. She will not be withdrawn from the study.) Failure to obtain an image will not be considered a breach of protocol and will not be reportable as such.

We will record multichannel EMG signals for 60 minutes for each subject. The subject will be eligible for compensation as outlined in section 10.1.

All health care management decision will be based on the standard obstetrical testing.

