### **14. DATA ANALYSIS AND MONITORING**

#### **14.1. Sample Size Determination**

This project is a pilot study to assess the reliability of uEMG compared to tocodynamometry for recording uterine contractions. Patient-to-patient variations include body habitus, uterine size, contraction strength and the amount of cervical dilation. We are not capable of controlling for all clinical variables, but assume that term patients carrying one baby in active labor will have contractions that are nearly uniform in producing uterine EMG signals. Thus, for these analyses, we assume that there are no subcategories of patient variables in the study population.

A sample size of 23 was determined using Odds Ratio statistics, assuming a 50% discrimination is clinically the minimum acceptable,  $\alpha=0.05$ ;  $\beta=0.8$ ; expected .75/.25 ratios. For each patient of 60 minutes of recording, we anticipate a minimum of 10 contractions could be observed. On average, we assume 10 contractions, for 23 patients, or 230 contractions.

However, to accommodate for patients who are enrolled in the study but who are subsequently excluded because of inability to complete the monitoring session, we will plan to recruit up to 50 patients.

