#### Contraction analysis

Whether subjects are in true labor or false labor, or perhaps transitioning into labor, will clinically be uncertain at the time of testing. The EMG data will be analyzed to predict the labor status, then the prediction will be correlated with the subject's outcome. Subjects who subsequently deliver within 24 hours will be considered to have been in labor. Those who deliver after 72 hours or more will be considered to be not-in-labor. Subjects who deliver between 24 and 72 hours will be considered to be transitioning into labor.

Endpoint 1.3 – Contraction analysis. Standard methods for EMG analysis of uterine signals utilizes the power of the EMG signal at each time point. The power values are then mathematically converted to mimic the time-dependent tracing of the Toco. In the PreTel analysis, up to 15 sensors will be distributed across the maternal abdomen to measure uEMG activity at each location. Each sensor will detect uEMG events as a function of time, but the events will not be scaled by power. Instead, the bioelectrical activity of each channel will be converted to an assessment of the presence or absence of a bioelectrical event at each time point and in each location. At each time point, events in all channels will be summed to yield a single time-dependent event tracing. This tracing will be mathematically converted to mimic the time-dependent tracing of the Toco. The PreTel Contraction Analysis software program will perform this analysis.

The PreTel Contraction Analysis will be compared against the Toco/IUPC tracing for sensitivity and specificity.

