### **14.3. Data and Safety Monitoring**

This study entails no more than minimal risk to the patient and fetus. As such, the study does not need a Data and Safety Monitoring committee. Oversight and monitoring of the conduct of the progress of the study will be the responsibility of the local investigators. Concern for the safety and wellbeing of the patients will be reported to the local investigators who will in turn contact the study Sponsor. Data validity and integrity will be handled by [name] following transfer of the de-identified uEMG data.

Endpoint 2.4a – Uterine contraction sensitivity and accuracy. A table of individual contractions identified by EMG, Toco and IUPC will be generated. Contractions detected by EMG or Toco within +/- 30 seconds of IUPC will be defined as True Positive (TP) detections. False Negative (FN) detections are defined as those contractions not detected by EMG or Toco, but detected by IUPC.

Sensitivity, S, for both EMG and Toco, will be calculated as

$$S(\text{EMG or Toco}) = \frac{\text{TP}}{\text{TP} + \text{FN}}$$

For training purposes, the data on laboring patients using non-invasive methods (i.e., not using IUPC) will be analyzed using a modified calculation for S where Toco positive will be used as a proxy gold standard.

$$\text{Modified S (EMG)} = \frac{\text{EMG positive}}{\text{Toco positive} + \text{apparent FN}}$$

Endpoint 2.4b – Contraction timing accuracy.

$\Delta t$  is a measure of the capability of each method to detect the timing of each contraction compared to gold standard.  $\Delta t$  is defined as the time the contraction peak is detected by EMG or Toco minus the time the peak is detected by IUPC in the corresponding contraction.

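### Section 5 compares EMG with tocometry by an undefined correlation R, Endpoint 1.3 uses sensitivity and specificity, and neither directly measures false contractions, the known EMG fault

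*Combined protocol and SAP*

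**What the plan says.** Section 5, in the text on triage patients, describes sending the EMG recordings and the paper monitor strip to the sponsor and then says "The EMG data will be compared to the tocometry data to determine correlation", or R value. It does not say whether R is taken per time point, per contraction or per woman, whether the traces may be aligned for lag, or what value would be acceptable.

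Section 14.2, Endpoint 1.3, builds a summed event trace from up to 15 sensors and adds "This tracing will be mathematically converted to mimic the time-dependent tracing of the Toco". The endpoint then reads "The PreTel Contraction Analysis will be compared against the Toco/IUPC tracing for sensitivity and specificity". It states no unit of scoring, matching window or denominator for specificity. R appears nowhere in Section 14.

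Endpoint 2.4a (printed under 14.3) is event-based: "Contractions detected by EMG or Toco within +/- 30 seconds of IUPC will be defined as True Positive (TP) detections". It defines true positives and false negatives only, so it yields sensitivity and no count of false positives.

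Section 1.2, on first-generation monitors, says "Reporting of false positive contractions is a problem with EMG reliability that is not seen with legacy methods".

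**The concern.** The aim in 14.1 is the reliability of uEMG against tocodynamometry in recording contractions. That is a question about events: which contractions were found, which were missed and which were invented. R answers a different question, namely how closely two waveforms move together. Specificity answers it poorly, because the absence of a contraction is not an event that can be counted. If time is counted instead, the long quiet intervals between contractions fill the denominator.

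The background presents false contractions as the weakness of earlier EMG monitors that clinicians are not used to handling. The study could report a favourable R or a favourable specificity for a device that still has this weakness, and no endpoint would show it directly.

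**Working it through.** **Inputs from the plan.** Recording length: "We will record multichannel EMG signals for 60 minutes for each subject", or 3,600 s. Contraction rate, from 14.1: "On average, we assume 10 contractions, for 23 patients, or 230 contractions"; 23 × 10 = 230 reproduces. The plan gives no figure for R, sensitivity or specificity. Its sample size reproduces as a one-sided, one-sample test of 0.50 against 0.75: ((1.645 × 0.500 + 0.842 × 0.433)/0.25)² = 22.5, rounded up to 23. That calculation has no bearing on R.

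**Assumptions, because the documents are silent.** The scenario is 10 real contractions, all detected on time, plus 5 false ones placed between them. Contraction width, pulse shape and the height of false pulses are assumed and varied.

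**Event scoring.** Sensitivity is 10/10 = 100%. Positive predictive value (PPV) is 10/15 = 67%. There are 5 false contractions per hour. None of these depends on contraction width.

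**Time-scored specificity**, 1 − (false seconds)/(quiet seconds):
- 60 s contractions: quiet time 3,600 − 600 = 3,000 s, false time 300 s, so 1 − 300/3,000 = 90%.
- 30 s contractions: 1 − 150/3,300 = 95%.
- 90 s contractions: 1 − 450/2,700 = 83%.

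**Waveform R** (zero-lag Pearson correlation of 1 Hz traces, Gaussian pulses). Let σ be the pulse SD (half-height width = 2.355σ), h the height of false pulses relative to true ones, and k = 5/10 = 0.5. With c = 2√π × 10σ/3,600 and no overlap between pulses,

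R = [1 − c(1 + kh)] / √{(1 − c)[1 + kh² − c(1 + kh)²]}.

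At σ = 15 s (half-height width 35 s), c = 0.148:
- Equal height, h = 1: 0.778/√(0.852 × 1.168) = 0.78.
- Half height, h = 0.5: 0.815/√(0.852 × 0.894) = 0.93.
- Double height, h = 2: 0.705/√(0.852 × 2.409) = 0.49.

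Wider pulses overlap, so the rest of the range was computed on the full traces. From 35 to 120 s half-height width, R falls from 0.78 to 0.61 at equal height and from 0.93 to 0.90 at half height.

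**Reading the results together.** The same device, wrong on one call in three, scores 83% to 95% on time-scored specificity. Its R is 0.90 or more if its false contractions are small. Only PPV and the hourly false count state the fault plainly.

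**The case against.** **The two analyses can coexist.** Section 5 is a procedural sentence and 14.2 is the analysis plan, so a descriptive correlation may sit beside event-level measures. This stands: the passages are not incompatible. What remains is that R is undefined and has no stated role.

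**No decision hangs on R.** There is no acceptance value, no endpoint uses R, and this is a pilot. This also stands, and it limits the weight of the point. A reader might infer that the device would be accepted on R, or that converting the EMG trace to resemble the Toco inflates R by itself. The documents support neither inference.

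**R does not always hide false contractions.** This is correct. With double-height false pulses R drops to 0.49 even at the narrowest width above. The claim is only that R can stay high.

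**A stronger reading is tempting and should not be made.** A reader might infer that R would rank a monitor with 3 false contractions per 10 above one that finds every contraction 30 s late. At zero lag, equal height and 60 s half-height width, R is indeed 0.83 against 0.61. But the order reverses in each of these cases:
- the delay is 10 s (R = 0.95 at that width);
- the half-height width is 100 s (0.78 against 0.80);
- false pulses are twice as tall (0.55 against 0.61 at 60 s);
- R is lag-aligned, when a uniformly late copy gives R near 1.

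Moreover, the ±30 s window is stated only against IUPC, in Endpoint 2.4a, and 30 s is its edge.

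**PPV against Toco charges Toco misses to the EMG.** This stands. Section 1.2 itself puts external monitoring as ineffective about 15% of the time. Restricting the analysis to interpretable reference time helps only in part.

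**Conclusion.** The point holds as an inexpensive improvement to the analysis. It is certain from the text that Section 5 names an R that Section 14 never uses, that Endpoint 1.3 gives specificity no unit or denominator, and that Endpoint 2.4a has no false-positive count. The size is conditional. The 90% specificity beside a PPV of 67% assumes scoring by time and 60 s contractions. The R values assume a zero-lag, time-point correlation of Gaussian pulses with false contractions no taller than real ones. Nothing here shows that R favours false contractions over delay; that order turns on delay, pulse width, pulse height and lag alignment, none of which the plan fixes.

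**What to change.** In Section 5, delete the R value or label it secondary and descriptive (stating the unit and how lag is handled), and refer to Endpoint 1.3 for the comparison.

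In Endpoint 1.3, state a matching window, score contraction by contraction, and report for each woman:
- sensitivity;
- positive predictive value;
- false contractions per hour of interpretable reference time.

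The last two replace specificity. Report Toco-referenced and IUPC-referenced results separately, and call the Toco-referenced values agreement, since some apparent false positives will be contractions that the Toco missed.

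The cost is a few sentences. Endpoint 2.4a already plans a table of individual contractions by EMG, Toco and IUPC, so no new data are needed. Care is unaffected, because Section 5 bases clinical decisions on standard monitoring and examination only.
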